7.16 Pharmacodynamic Assessments and Schedule

The pharmacodynamic parameter GIR will be determined from the concentration-time data for all evaluable subjects.

Serum C-peptide and endogenous human insulin will be analyzed out of the PK sample at all PK sampling timepoints as stated in the PK sampling schedule. Instructions for PK sample processing and shipment are provided in section [7.15](#).

Please see [Table 7-2](#) for PK Blood Sampling Schedule.

7.17 Tolerability Assessments

After injection of the study drug, the injection site will be marked with a pen. Assessment of study drug injection site will be performed at 15 (± 3) min, at 60 (± 10) min and at 720 (± 30) min after dosing.

The local reaction from the injection site, the insertion site, and the adhesive will be evaluated quantitatively using a Draize scale or similar scale by qualified study staff. If an injection site reaction like pain on palpation, itching, erythema, edema, induration is observed, it must be recorded as an AE and then will be evaluated using the following scale:

Erythema will be evaluated as follows:

- 0 – No erythema
- 1 – Very slight erythema (barely perceptible)
- 2 – Well-defined erythema
- 3 – Moderate to severe erythema
- 4 – Severe erythema (beet redness) to slight eschar formations (injuries in depth)

Edema will be evaluated as follows:

- 0 – No edema
- 1 – Very slight edema (barely perceptible)
- 2 – Slight edema (edges of area well defined by definite raising)
- 3 – Moderate edema (raised approximately 1 mm)
- 4 – Severe edema (raised more than 1 mm and extending beyond the area of exposure)

The diameter of the affected area will be measured with a paper measurement in cm and the condition of the injection site will be recorded. Digital photography will be used to document all positive injection site reactions. In case of clinically significant injection site reactions, subjects may undergo a dermatological consultation.

7.18 Blood Volume

Total blood sampling volume for subjects will approximately be 390 mL.

Even in case of further unexpected blood sampling, extension of blood sampling period or necessary retesting, sampling volume will not exceed 420 mL.

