7.14.2 Glucose Clamp Set-Up

The Biostator is set up with infusion lines for blood glucose management. One 0.9% sodium chloride (NaCl) and two Dextrose 20% (D20) IV infusion lines are connected via an infusion module. All three lines are linked together using three-way valves which are then connected to the subject through an IV catheter on the contralateral arm (contralateral and ipsilateral are defined as relative to Biostator). A second IV line is inserted (generally the dorsal hand vein, the lateral wrist vein of ipsilateral arm or any peripheral arm vein) and setup through a different Biostator module using a Double Lumen Catheter (DLC). One lumen is used for a continuous blood sample draw at an estimated rate of 2 mL/hr; while the other lumen, is used to infuse a low concentration of heparinized saline solution to the catheter tip where it is then mixed with the blood drawn. This mix avoids sample clotting within the tubing. The DLC vein site is covered by a heating pad for arterialization of venous blood flow. The Biostator system programming and operation is done per [REDACTED] standard operating procedures. An external D20% IV line is connected to the infusion lines. This infusion is manually operated by the technicians running the clamp in coordination with the medical staff and is used (e.g., in case the GIR delivered by the Biostator is insufficient).

As a background validation with a second methodology for safety, the standardized measurements of the Biostator will be verified on a regular basis using the YSI reference (YSI 2300 STAT or equivalent YSI Glucose Analyzer; Yellow Springs Instruments, Ohio, USA) device at approximately every 30 minutes.

Please see [Appendix B](#) for a detailed Clamp Sampling Schedule.

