7.14.3 Glucose Clamp Procedure

During the study, subjects will undergo two euglycemic clamp procedures, one per treatment period. All clamp procedures will be performed identically.

Subjects will be connected to the Biostator through peripheral arm veins as described in section 7.14.2. The clamp procedure will follow instructions described in section 4.2.

The Biostator will be turned on and programmed. The body weight in kilograms used for Biostator programming on both clamps, corresponds to the weight measurement obtained on Day 1 of Treatment Period 1. At least one hour before dosing ($t = -60$ min), the Biostator will start recording data. During this pre-dose monitoring period, glucose readings are obtained and analyzed with a YSI 2300 STAT or equivalent YSI Glucose Analyzer (Yellow Springs Instruments, Yellow Springs, Ohio, USA) at the following time points relative to the start of the trial drug infusion: -60, -30, -20 and -10 minutes. The average of blood glucose values prior to dosing (-30 min, -20 min, -10 min) correspond to each subject's individual BASELINE glycemic level. The glucose CLAMP TARGET level is determined by subtracting 5 mg/dL from the BASELINE glycemic level (Target level = BASELINE - 5 mg/dL). Subjects whose differences between initial fasting BG values (-30, -20, -10 min) exceed the limit of 10 mg/dL will be rescheduled to another day. Additionally, subjects will not be dosed if mean fasting plasma glucose is < 75 mg/dL due to proximity to overt hypoglycemia or > 99 mg/dL. Subjects may be re-scheduled once to come back to the site on a later day and may be dosed if the mean fasting plasma glucose is ≥ 75 mg/dL or ≤ 99 mg/dL prior to dosing.

At $t = 0$ -min, the investigational product will be administered per randomization schedule.

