7.15 Pharmacokinetic Assessments and Schedule

Blood for PK analysis of the IP, the human insulin analog, will be collected at the time points indicated in the SOE ([Appendix A](#)) and follow the PK blood sampling schedule below.

At each sampling time point, 1.0 mL of blood will be discarded for waste (utilizing a throw away tube). Thereafter, one 6.0 mL whole blood sample per scheduled time point will be collected to provide a minimum of 1.5 mL of serum for PK measurements and 1.5 mL of serum as a secondary back-up sample. Instructions for sample processing and shipment are provided below.

Table 7-2 PK Blood Sampling Schedule (6 mL per sample)

Seq. #	Scheduling	Time window	Sample No., "XX"	#	Scheduling	Time window	Sample No., "XX"
1	-60 min	± 5 min	01	15	75 min	±3 min	15
2	-30 min		02	16	80 min	±5 min	16
3	0 min	±1 min	03	17	90 min		17
4	5 min		04	18	105 min		18
5	10 min	±2 min	05	19	120 min		19
6	20 min		06	20	150 min	±10 min	20
7	25 min	±3 min	07	21	180 min		21
8	30 min		08	22	210 min		22
9	40 min		09	23	4 h		23
10	50 min	±3 min	10	24	5 h	±20 min	24
11	55 min		11	25	6 h		25
12	60 min		12	26	8 h		26
13	65 min		13	27	10 h		27
14	70 min		14	28	12 h		28
Total							28 (168mL)

PK Sample Processing and Shipment Instructions are described below:

(1) Sampling Procedure

A catheter will be inserted into one of the antecubital region veins for blood sampling. Alternatively, collection from a vein from the hand or forearm for easier access or via venipuncture is also acceptable. PK blood draws should use the opposite arm of the glucose infusion/clamp. Preferably, the arm with better venous access will be used for PK samplings, and the opposite arm for the glucose infusion/clamp. In case of extraordinary situations, such as IV infiltration etc, the PK samples could be collected from the arm of the clamp, for safety reason.

After each blood sample collection, a catheter flush will be performed to avoid catheter clot formation and prevent interference between samples.

At each PK sampling point, the first 1 mL of blood will be discarded for waste (utilizing a disposable tube), and blood samples (~6 mL per sample), will be collected in a serum separation tube and left to stand at room temperature for 30 - 60 minutes. Each sample will be centrifuged at 2-8°C, 1,000-1,300 g for 20 minutes.

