APPENDIX A

Schedule of Events (SOE)

ASSESSMENT	SCREEN	IN-HOUSE PERIOD 1	WASH-OUT	IN-HOUSE PERIOD 2	FOLLOW-UP ¹
IP administration		X		X	
Informed consent	X				
Assess eligibility criteria	X				
Demography	X				
Medical history	X				
History of prior Insulin exposure/use	X				
Sequestered in clinic		X		X	
Physical examination (PE)	X				X
Hematology, serum chemistry & urinalysis ⁵	X				X
HbA1c	X				
Coagulation	X				
TSH	X				
Hep B, Hep C, HIV	X				
FSH if postmenopausal	X				
Pregnancy test(serum)	X				
Pregnancy test(urine)		X		X	X
Urine drug screen & alcohol breath test	X	X		X	X
Weight	X	X		X	
Height, BMI	X				
Vital signs	X	X ²		X ²	X
12-lead ECG	X	X ³		X ³	X
Standardized meals		X		X	
Record concomitant medications	X	X		X	X
Record AEs	X	X		X	X
Assess check-in criteria		X		X	
Randomization		X			
Injection site assessment		X ⁴		X ⁴	
Clamp procedure		X		X	
PK/PD assessments		X		X	
Blood glucose (YSI)	X	X		X	

¹To be performed after second dosing or at early termination

²On each Day 1, vital signs to be measured 15 (± 5) min pre-clamp/pre-dose and at 5(± 3) min, 60 (± 10) min, 180 (± 20) min and 720 (± 30) min post-dose.

³On each day 1, ECG 15 (± 5) min pre-clamp/pre-dose and at 5 (± 3) min, 60 (± 10) min, 180 (± 20) min and 720 (± 30) min post-dose.

⁴Assessment of reaction at 15 min, 60 min and 720 min post-dose.

⁵Unscheduled visits for safety lab testing are allowed during COVID-19 pandemic.

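### The 390 mL total and 420 mL ceiling in protocol 7.18 do not cover the blood the protocol schedules (about 444 mL before laboratory and YSI samples), and a repeat clamp with its PK series breaks the ceiling on any reading

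*Protocol*

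**What the plan says.** Protocol 7.18 consists of two statements. The first is "Total blood sampling volume for subjects will approximately be 390 mL". The second is "Even in case of further unexpected blood sampling, extension of blood sampling period or necessary retesting, sampling volume will not exceed 420 mL". Neither is itemised, and neither excludes any kind of draw.

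The draws are described elsewhere in the protocol:

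- **PK tubes and discards (7.15).** "At each sampling time point, 1.0 mL of blood will be discarded for waste"; after that, "one 6.0 mL whole blood sample per scheduled time point will be collected". Table 7-2 lists 28 time points per visit and totals them as 168 mL, which is the tubes without the discards.
- **Biostator (7.14.2).** "One lumen is used for a continuous blood sample draw at an estimated rate of 2 mL/hr". The other lumen carries heparinized saline. Under 7.14.3, "the Biostator will start recording data" no later than 60 minutes ahead of the injection. The clamp then runs 12 hours, and 4.1 plans two clamps per subject.
- **YSI reference.** Biostator readings are checked against the YSI "device at approximately every 30 minutes" (7.14.2). No sample volume is given.
- **Safety laboratory.** Appendix A lists "Hematology, serum chemistry & urinalysis" at screening and follow-up, with further blood tests at screening. No tube volumes are given.

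Section 7.14.4 says that a clamp with a CV or a deviation from target of 12% or more should be repeated where feasible, or the subject replaced, after the investigator and sponsor have discussed it. It does not refer to 7.18.

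**The concern.** Section 7.18 is the only cumulative limit on blood taken in this protocol, and it is worded to hold even when something unplanned happens. A limit of that kind has to sit above the planned volume. If ordinary sampling already reaches or passes it, it cannot act as a stop for retests, unscheduled laboratory visits or a repeat clamp, and the site has no usable number for judging whether a repeat under 7.14.4 is feasible. The IRB would also be judging the burden on healthy volunteers from a figure that is too low or is undefined.

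**Working it through.** **Inputs.** 28 PK time points per visit, 6 mL per tube and 1 mL discard (7.15, Table 7-2); device draw 2 mL/h (7.14.2); device running from -60 to 720 min, so 13 h (7.14.3 and Appendix B); two visits (4.1).

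**Scheduled draws with a stated volume, two visits**

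- PK tubes: 2 × 28 × 6 = 336 mL
- Discards: 2 × 28 × 1 = 56 mL
- Device: 2 × 2 mL/h × 13 h = 52 mL
- Sum: 336 + 56 + 52 = 444 mL

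**Can the plan's 390 mL be reproduced?** Not from the full list. Three partial sums come close:

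| Items counted | mL | Left out |
|---|---|---|
| PK tubes + discards | 392 | device, laboratory, YSI |
| PK tubes + device | 388 | discards, laboratory, YSI |
| PK tubes + 54 mL for laboratory (and possibly YSI) blood | 390 | discards, device |

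The documents do not say which, if any, was used. The 54 mL in the last row is only the remainder, 390 - 336.

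**Size of the gap**

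- Against the total: 444 - 390 = 54 mL (13.8%).
- Against the ceiling: 444 - 420 = 24 mL (5.7%).
- Tubes-only reading: 390 + 56 + 52 = 498 mL is drawn, so 108 mL is not counted.

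**Sensitivity to the device draw**

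- 12 h: 392 + 48 = 440 mL. 14 h: 392 + 56 = 448 mL.
- Half of the 2 mL/h is blood, over 13 h: 392 + 26 = 418 mL, which leaves 2 mL under the ceiling for all laboratory and YSI blood.
- No device draw counted: 392 mL, which leaves 28 mL.

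**Laboratory and YSI blood (assumed volumes; the documents give none)**

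- Laboratory tubes of 20 to 50 mL in total: 464 to 494 mL, which is 10.5% to 17.6% above 420.
- YSI samples: 29 per visit (-60, -30, -20, -10 and 0 min, then every 30 min to 720), 58 in total. At 0.25 to 1 mL each they add 14.5 to 58 mL to the 444 mL, giving 458.5 to 502 mL without laboratory tubes.

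**Repeat clamp**

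- Stated total plus one more set of PK tubes: 390 + 168 = 558 mL, 138 mL (32.9%) above 420.
- PK tubes alone, three series and nothing else: 336 + 168 = 504 mL, still above 420.
- All items: one clamp takes 168 + 28 + 26 = 222 mL, so 444 + 222 = 666 mL.
- The reserve in 7.18 is 420 - 390 = 30 mL, which is five 6 mL tubes out of the 28 in a series.

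**The case against.** The strongest reply is that 7.18 counts tubes only. Table 7-2 does so: its 168 mL omits the discards described in the same section. On that convention 336 mL of PK tubes leaves 54 mL for laboratory and YSI blood, and 390 mL is a coherent budget. This is possible, and it stands as a reason not to say that the sponsor's sum is an arithmetic slip. But 7.18 speaks of a total and does not state the convention, 7.14.2 calls the device line a blood sample draw, and the omitted blood still leaves the subject.

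A reader might infer that every subject who completes both visits passes 420 mL before a single laboratory tube. The documents do not support that without conditions. It requires counting every discard in full as blood, although the catheter is flushed after each sample. It also requires more than 28 of the 52 mL of device draw to be blood; that rate is an estimate, and the line also carries saline. At half rate the sum is 418 mL.

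A reader might also infer that rescheduled visits alone use up the reserve. A reschedule decided on fasting glucose costs two PK draws with discards and an hour of device draw, 2 × 7 + 2 = 16 mL, so two cost 32 mL against 30 mL. That comparison mixes accounting bases: on tubes only, two reschedules cost 2 × 2 × 6 = 24 mL and fit.

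On the repeat clamp, 7.14.4 makes the repeat conditional, offers replacement, and does not say that all 28 PK samples are drawn again. Replacement is indeed a compliant route. But SAP 5.2.3 (Eqs 29 and 30) multiplies the smoothed GIR by the insulin aspart fraction at the same time point, so a repeat clamp needs its own PK series for the net insulin aspart endpoints. For the same reason, a rule that PK from the failed visit be kept would pair one day's GIR with another day's insulin levels in those equations; it is not a way around the volume.

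Finally, the laboratory manual cited in 3.3 may hold an itemised volume. That would help, but it would not alter what 7.18 states.

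**Conclusion.** The figures in 7.18 do not match the sampling the protocol describes. With all stated draws counted, the planned volume is about 444 mL (440 to 448 mL for 12 to 14 h of device draw at the full 2 mL/h), above both 390 and 420 mL before laboratory and YSI blood. With the device draw left out entirely, the sum of 392 mL still uses all of the stated total. On the tubes-only reading the stated total may be right, but up to about 108 mL is drawn outside it.

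The conflict with 7.14.4 does not depend on the reading: a repeat clamp with its PK series gives at least 558 mL on the protocol's own total. It assumes only that the repeat includes the PK series.

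Nothing here shows that the volume is unsafe, and neither the primary analysis nor the sample size is touched. The correction should be made because a stated limit for healthy volunteers cannot do its job as written.

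**What to change.** **Section 7.18.** Replace the two figures with an itemised total: PK tubes (336 mL), discards (56 mL), device draw (about 52 mL), YSI samples (number × volume), and screening and follow-up laboratory tubes (volumes from the laboratory manual). Set the ceiling at that total plus a stated reserve for retests and rescheduled visits.

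**Section 7.14.4.** Allow a repeat clamp only if the subject's cumulative volume stays within the 7.18 ceiling; otherwise replace the subject. A full repeat costs about 222 mL, so the sponsor has to choose: either the reserve is large enough to cover one, or replacement becomes the usual route.

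**Cost.** An itemised line and one conditional phrase. The sampling schedule, sample size and SAP do not change. The downside is that the stated volume rises and the IRB must see the corrected figure.

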8.0 ADVERSE EVENTS

8.1 Definitions

8.1.1 Adverse Event (AE)

An AE is any undesirable and unintended medical event occurring to a subject in a clinical study, whether or not related to the study products. This includes events from the first study related activity after the subject has signed the informed consent and until post treatment follow-up period as defined in the protocol. The following should not be recorded as AEs, if recorded as medical history/concomitant illness on the eCRF at Screening:

- Pre-planned procedure, unless the condition for which the procedure was planned has worsened from the first study related activity after the subject has signed the informed consent
- Pre-existing conditions found as a result of Screening procedures
- Pre-existing events that has not worsened in intensity or frequency from baseline

8.1.2 Treatment Emergent Adverse Event (TEAE)

A treatment-emergent AE (TEAE) is defined as any clinically significant event not present before exposure to study drug or any event already present that worsens in either intensity or frequency after exposure to study drug.

8.1.3 Clinical Laboratory Event

A clinical laboratory AE is any clinically significant laboratory abnormality that suggests a disease and/or organ toxicity and is of a severity, which requires active management, (i.e. change of dose, discontinuation of study product, more frequent follow-up or diagnostic investigation).

A laboratory re-test and/or continued monitoring of an abnormal value is not considered an intervention. In addition, repeated or additional noninvasive testing for verification, evaluation or monitoring of an abnormality is not considered an intervention.

8.1.4 Unexpected Adverse Event/ Unexpected Suspected Adverse Reaction

An unexpected AE/unexpected suspected adverse reaction is an AE or suspected adverse reaction that is not listed in the Investigator Brochure or Protocol, as occurring with a class of drugs or as anticipated from the pharmacological properties of the drug, but are not specifically mentioned as occurring with the particular drug under investigation, or is not listed at the specificity or severity

that has been observed; or, if an Investigator Brochure is not required or available, is not consistent with the risk information described in the general investigational plan or elsewhere in the current application.

8.1.5 Serious Adverse Event (SAE)/ Serious Suspected Adverse Reaction

An SAE is defined as any untoward medical occurrence that at any dose:

- (1) Results in death.
- (2) Is life threatening.
 - The term “life threatening” refers to an event in which the subject was at risk of death at the time of the event; it does not refer to an event that hypothetically might have caused death if it were more severe.
- (3) Requires inpatient hospitalization or prolongation of existing hospitalization. Hospitalization is defined as an admission of greater than 24 hours to a medical facility and does not always qualify as an AE.
- (4) Results in persistent or significant disability/incapacity.
- (5) Leads to a congenital anomaly/birth defect.
- (6) Is an important medical event that satisfies any of the following:
 - May require intervention to prevent items 1 through 5 above.
 - May expose the subject to danger, even though the event is not immediately life threatening or fatal or does not result in hospitalization.

8.1.6 Life-Threatening Adverse Event/Life-Threatening Suspected Adverse Reaction

A life-threatening AE/life-threatening suspected adverse reaction, in the view of either the Investigator or Sponsor, places the patient or suspect at immediate risk of death. It does not include an adverse reaction that, had it occurred in a more severe form, might have caused death.

The determination of whether an AE is life threatening can be based on the opinion of the Investigator or Sponsor. If either, the Sponsor or investigator believes that the event is serious or life threatening, the event must be considered serious and evaluated by the Sponsor for expedited reporting (21 CFR 312.32(a) and 312.32(c)(1)).

8.1.7 Severity of AEs

The different categories of intensity (severity) are characterized as follows:

Mild:	The event is transient, easily tolerated by the subject and does not affect the subject's daily activities.
Moderate:	The event causes the subject discomfort and interrupts the subject's usual daily activities.
Severe:	The event is incapacitating and causes considerable interference with the subject's usual activities.

8.1.8 Relationship to Study Treatment

Very Likely Related:	There is clear evidence that the event is related to the use of the IP. The AE follows a reasonable temporal sequence from administration of a drug (including the course after withdrawal of the drug), or for which possible involvement of the drug can be argued.
Probably Related:	The AE follows a reasonable temporal sequence from the IP administration, and there is a high degree of certainty that the AE is related to study drug administration (eg, it represents a known reaction to the IP or other drugs in its class or is predicted by the known pharmacological properties of the drug).
Unknown:	The event follows a reasonable temporal sequence from the IP administration, and cannot be reasonably explained by the subject's clinical state or other causes (eg, disease under study, concurrent diseases, or concomitant medications).
Unlikely Related:	An event for which an alternative explanation is more likely (eg, concomitant medications or ongoing medical conditions) or the temporal relationship to IP administration and/or exposure suggests that a causal relationship is unlikely (for reporting purposes, Unlikely will be grouped together with Not Related)
Definitely Not Related:	An AE that does not follow a reasonable temporal sequence from administration of IP and/or that can reasonably be explained by other factors, such as underlying diseases, complications, concomitant drugs and concurrent treatments.

8.2 Procedures

8.2.1 Collection and Recording of AEs

Collection of all AEs (serious AEs and non-serious AEs) will commence from the time the subject signs the informed consent to participate in the study until the post-treatment follow-up visit. At each study visit, the Investigator will assess whether any subjective AEs have occurred. In order to avoid bias in eliciting AEs, a non-specific question, such as “How have you been feeling since your last visit?” may be asked. Subjects may report AEs occurring at any other time during the study.

All subjects experiencing AEs, whether considered associated with the use of the study medication or not, must be monitored and given appropriate medical treatment at the discretion and judgement of the Investigator until the symptoms subside and any clinically relevant changes in laboratory values have returned to baseline or until there is a satisfactory explanation for the changes observed. All AEs will be documented in the AE page of the eCRF, whether or not the Investigator concludes that the event is related to the drug treatment. The event term, start and stop dates, severity, action taken with study drug and outcome, will be documented, along with the Investigator’s opinion of the causal relationship between the event and the IP.

